10.5 DISCONTINUATION/WITHDRAWAL OF SUBJECTS FROM STUDY TREATMENT

Subjects have the right to voluntarily discontinue study treatment or withdraw from the study at any time for any reason without any consequences. The investigator has the right to discontinue a subject from study treatment or withdraw a subject from the study at any time if it is in the best interest of the subject.

Subjects must discontinue the investigational medicinal product(s) and be withdrawn from the study for any of the following reasons:

- Withdrawal of consent by the subject
- Any medical condition that the investigator or sponsor determines may jeopardize the subject's safety if she or he continues receiving the study treatment
- Pregnancy
- Ineligibility (either arising during the study or retrospectively having been overlooked at screening)
- An adverse event which requires discontinuation of the study medication
- Treatment failure and disease progression
- Lack of compliance with the study and/or study procedures (e.g., dosing instructions, study visits).
- Lost to follow-up following at least 3 documented attempts to contact any subject before defining them as lost to follow-up.

All subjects who discontinue should comply with protocol specified follow-up procedures. The only exception to this requirement is when a subject withdraws consent for all study procedures.

If a subject is withdrawn before completing the study, the reason for withdrawal must be entered on the appropriate case report form (CRF) page.

If a subject is withdrawn due to an adverse event, the investigator will arrange for follow-up visits until the adverse event has resolved or stabilised.

11.0 TREATMENT OF TRIAL SUBJECTS

11.1 DESCRIPTION OF STUDY TREATMENT(S)

Active therapy – Fampryra (fampridine) oral capsules 10 mg BID. (Supplied by Biogen Idec Ltd.)

Placebo – an identical placebo capsule administered BID will also be used (supplied by Biogen Idec)

11.2 FORMULATION, PACKAGING, AND HANDLING

Fampryra and Fampryra identical placebo are produced in tablet form for twice daily oral use. They will be supplied in a box of 14 tablets (one weeks supply). There is no secondary packaging.

The product label will look as follows:

FAMPYRA® 10MG TABLETS OR PLACEBO

Fampridine 10mg tablets or placebo

14 tablets

Take ONE tablet TWICE daily

To be taken orally. For clinical trial use only.

Keep out
of reach of
children.
Store at
room
temperature
in original
container.

Patient Name/ID No. _____
Date _____

Product Code No. _____ Expiry Date

Principal Investigator: [name]. Trial Sponsor: SVUH
Site: St. Vincent's University Hospital. Trial Ref. No. SVUHneur002

Name and address of supplier of Fampyra and Placebo medication:

Biogen Idec Ltd. [name],
[name],
[name],
[name],
[name],
Ireland

Name and Address of Pharmacy who will label the study treatment:

Pharmacy Department
St. Vincent's University Hospital,
[name]

11.3 STORAGE AND DISPOSITION OF STUDY TREATMENTS(S)

The Fampyra and Placebo tablets will be stored on separate shelves of a locked press at room temperature in the Pharmacy Department of St. Vincent's University Hospital until dispensed to subjects. Returns will be stored by the study nurse in a secure location in the Neurology department until authorised for destruction.

The temperature of study medications will be monitored during shipment to SVUH. On arrival to SVUH, temperature will be monitored and recorded daily on a temperature log. Subjects will be advised to store the study drug at room temperature.

The study treatments are for investigational use only and are only to be used within the context of this trial.

11.4 ACCOUNTABILITY OF THE STUDY TREATMENT(S)

The investigator is responsible for the control of the treatment under investigation. Adequate records for receipt and disposition of the IMP will be maintained.

The study medication will be supplied to pharmacy by Biogen Idec Ltd. and retrieved at the end of the study.

The investigator will use a standard prescription form and the investigator/research nurse will collect the medication from the pharmacy on the day of dosing.

Maintaining dispensing and return records will assess accountability and subject compliance with study treatments. A master accountability investigational product log will be maintained for each product. This will record the total quantity received and dispensed to each subject. Two single subject investigational product accountability logs will also be maintained for each subject, one for medication dispensed and one for medication returned.

The study nurse will monitor compliance at each return visit.

Prior consent will be obtained from the study sponsor to allow destruction of returns and unused excess stock provided by Biogen Idec Ltd. It will be destroyed according to the SVUH Whole Hospital Waste Disposal and Management Policy, SVUH HS POL 01, May 2011 and a receipt of destruction will be provided to the sponsor.

10.5 ASSESSMENT OF COMPLIANCE

The investigator is responsible for ensuring that the study treatment is administered in compliance with the protocol. Maintaining dispensing records will assess subject compliance.

10.6 OVERDOSE OF STUDY TREATMENT

Patients who overdose will be admitted to SVUH and provided with supportive care. Repeated seizure activity will be treated with benzodiazepine, phenytoin, or other appropriate acute anti-seizure therapy.

10.7 PRIOR AND CONCOMITANT THERAPY

Any medication, other than the study medication taken during the study will be recorded in the CRF from the second baseline visit to the last visit.

Permitted medications/non- investigational medicinal products will include treatments of acute MS exacerbations including corticosteroids (high dose IV or short course of oral steroids) and symptom therapies such as baclofen. Antibiotics will be permitted for intercurrent infections.

Prohibited medications:

Concomitant use of medicinal products that are inhibitors of Organic Cation Transporter 2(OCT2) for example cimetidine are prohibited for the duration of the study. Concurrent treatment with other medicinal products containing fampridine (4- aminopyridine) is also prohibited.

12.0 SAFETY REPORTING

The safety and tolerability of the IMP will be evaluated throughout the study e.g. by AEs and neurological examination.

12.1 DEFINITIONS

12.1.1 Adverse event (AE)

Any untoward medical occurrence in a patient or clinical trial subject administered a medicinal product and which does not necessarily have a causal relationship with this treatment.

An adverse event can therefore be any unfavourable and unintended sign (including an abnormal laboratory finding, for example), symptom or disease temporally associated with the use of a medicinal product, whether or not considered related to the medicinal product

12.1.2 Adverse reaction (AR)

All untoward and unintended responses to a medicinal product related to any dose.

The phrase ‘responses to a medicinal product’ means that a causal relationship between a study medication and an AE is at least a reasonable possibility, i.e., the relationship cannot be ruled out.

All cases judged by either the reporting medically qualified professional or the sponsor as having a reasonable suspected causal relationship to the study medication qualify as adverse reactions.

12.1.3 Serious adverse event

Any untoward medical occurrence or affect that at any dose:

- Results in death
- Is life-threatening*
- Requires hospitalisation or prolongation of existing hospitalisation
- Results in persistent or significant disability or incapacity
- Is a congenital anomaly or birth defect
- Important medical events**

*Regarding a life-threatening event, this refers to an event in which the subject was at risk of death at the time of the event; it does not refer to an event, which hypothetically might have caused death if it were more severe.

**Some medical events may jeopardise the subject or may require an intervention to prevent one of the above characteristics/consequences. Such events (hereinafter referred to as ‘important medical events’) should also be considered as ‘serious’ in accordance with the definition

12.1.4 Severe adverse events

The term ‘severity’ is used here to describe the intensity of a specific event. This has to be distinguished from the term ‘serious’.

12.1.5 Suspected unexpected serious adverse reactions

An adverse reaction, the nature or severity of which is not consistent with the applicable product information (e.g. investigator’s brochure for an unauthorised investigational medicinal product or summary of product characteristics for an authorised medicinal product).

12.2 EVALUATIONS OF AES AND SAES

Seriousness, causality, severity and expectedness will be evaluated.

12.2.1 Assessment of seriousness

The investigator will make an assessment of seriousness as defined in section 12.1.4.

12.2.2 Assessment of causality

All adverse events judged by either the investigator or the sponsor as having a reasonable suspected causal relationship to an investigational medicinal product qualifies as adverse reactions.

The sponsor should not downgrade the causality assessment given by the investigator.

The investigator/sponsor must make an assessment of whether the AE/SAE is likely to be related to treatment according to the following definitions:

Unrelated

Where an event is not considered to be related to the study medication.

Possibly

Although a relationship to the study medication cannot be completely ruled out, the nature of the event, the underlying disease, concomitant medication or temporal relationship makes other explanations possible.

Probably

The temporal relationship and absence of a more likely explanation suggest the event could be related to the study medication.

All AEs/SAEs judged as having a reasonable suspected causal relationship (e.g. possibly, probably) to the study medication will be considered as ARs/SARs.

All AEs/SAEs judged as being related (e.g. possibly, probably) to an interaction between the study medication and another medication will also be considered to be ARs/SAR.

Alternative causes such as natural history of the underlying disease, concomitant therapy, other risk factors and the temporal relationship of the event to the treatment should be considered.

12.2.3 Assessment of severity

The investigator will make an assessment of severity for each AE/SAE and record this on the CRF according to one of the following categories:

Mild

An event that is easily tolerated by the subject, causing minimal discomfort and not interfering with every day activities.

Moderate

An event that is sufficiently discomforting to interfere with normal everyday activities.

Severe

An event that prevents normal everyday activities.

12.2.4 Assessment of expectedness

The expectedness of an adverse reaction will be determined by the sponsor according to the reference document e.g. the investigator's brochure for a non-authorized investigational medicinal product, or the summary of product characteristics for an authorized medicinal product, which is used according to the terms and conditions of the marketing authorisation.

12.2.5 Emergency unblinding procedures

The principle investigator should be contacted if emergency unblinding is required. They will be provided with a sealed envelope (with a signature and date across the seal) containing the randomization code, active product codes and placebo product codes. The envelope may be opened if emergency unblinding is required.

12.3 REPORTING PROCEDURES FOR ALL ADVERSE EVENTS

All AEs occurring during the study observed by the investigator or reported by the subject, whether or not attributed to the study medication, will be recorded on the CRF.

The following information will be recorded: description, date of onset and end date, severity, and assessment of relatedness to the study medication, other suspect medication or device and action taken. Follow-up information should be provided as necessary.

AEs considered related to the study medication as judged by an investigator or the sponsor will be followed until resolution or until the event is considered stable. All related AEs that result in a subject's withdrawal from the study or are present at the end of the study, should be followed up until a satisfactory resolution occurs.

It will be left to the investigator's clinical judgment whether or not an AE is of sufficient severity to require the subject's removal from treatment. A subject may also voluntarily withdraw from treatment due to what he or she perceives as an intolerable AE. If either of these occurs, the subject must undergo an end-of-study assessment and be given appropriate care under medical supervision until symptoms cease or the condition becomes stable.

The severity of events will be assessed on the following scale: mild, moderate, and severe.

The investigator will assess the relationship of AEs to the study medication.

Any pregnancy occurring during the clinical study and the outcome of the pregnancy should be recorded and followed-up for congenital abnormality or birth defect.

12.4 REPORTING PROCEDURES FOR SERIOUS ADVERSE EVENTS

The investigator will report all serious adverse events immediately to the sponsor except for those that the protocol or investigator's brochure identifies as not requiring immediate reporting. The immediate report will be followed by detailed, written reports. The immediate and follow-up reports will identify subjects by unique code numbers assigned to the latter.

The investigator will make the immediate report within a very short period of time and under no circumstances should this exceed 24 hours following knowledge of the serious adverse event.

All SAE information must be recorded on an SAE forms and sent expeditiously to the sponsor. Additional information received for a case (follow-up or corrections to the original case) need to be detailed on a new SAE form and sent expeditiously to the sponsor.

The sponsor will keep detailed records of all adverse events, which are reported to him by the investigator or investigators.

In cases where reporting is not required immediately the investigator will report within the appropriate time frame, taking account of the specificities of the trial and of the serious adverse event, as well as possible guidance in the protocol or the IB.

The sponsor will report all SUSARs to the competent authorities (the IMB in Ireland) and the ethics committees concerned. Fatal or life-threatening SUSARs must be reported within **7 days**. SUSARs which are not fatal and not life threatening are to be reported within **15 days**. The sponsor will also inform all investigators concerned of relevant information about SUSARs that could adversely affect the safety of subjects.

If the initial report is incomplete, e.g. if the sponsor has not provided all the information/assessment within seven days, the sponsor will submit a completed report based on the initial information within an additional eight days.

If the sponsor receives significant new information on an already reported case, the clock starts again at day zero, i.e. the date of receipt of new information. This information will be reported as a follow-up report within 15 days.

In addition to the expedited reporting above, the sponsor shall submit once a year throughout the clinical trial or on request, a safety report to the competent authority (the IMB in Ireland) and ethics committees. The annual safety report will be presented in the DSUR format as per ICH guideline E2F - Note for guidance on development safety update reports. This is a legal requirement

12.5 DATA SAFETY MONITORING BOARD (DSMB)

Due to the short duration of this study the Trial Steering Committee has determined that a DSMB is not needed.

12.6 PREGNANCY

Pregnancy is not considered an AE or SAE however the investigator will collect pregnancy information for female trial subjects or female partners of male trial subjects who become pregnant while participating in a study.

The investigator will record the information on a Pregnancy Notification Form and submit this to the sponsor.

Any pregnancy that occurs in a trial subject or a trial subject's partner during a trial will be followed to outcome.

13.0 STATISTICS

13.1 DESCRIPTION OF STATISTICAL METHODS

Outcome will be assessed using the Wilcoxon Signed Rank test to establish whether there is a difference between the paired 'on treatment' outcome measures for each individual.

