9.0 STUDY OBJECTIVE

The objective of this study is to assess the affect of PR-fampridine medication compared to placebo for upper limb function in patients with progressive multiple sclerosis

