9.4 PRIMARY AND SECONDARY/ EXPLORATORY ENDPOINTS/OUTCOME MEASURES

Primary endpoint:

The primary end point will be identifying an upper limb responder to fampridine defined as a patient with both of the two “on treatment” 9-HPT assessments (assessments 4 & 5 or 7 & 8) improving 20% from the average of the baseline assessments (1, 2 & 3).

Secondary endpoints:

A secondary measure of upper limb responsiveness will be defined as a 20% improvement in from baseline in the average time taken to complete all seven tasks on the JTT “on treatment” (assessments 4 & 5 or 7 & 8) compared with baseline assessments (assessments 1,2 & 3).

A mobility responder to Fampridine will be defined as a patient with both of the two “on treatment” T25FW assessments (assessments 4 & 5 or 7 & 8) being better than the maximum of any of the four “off treatment” assessments (assessments 1, 2, 3, & 9). Otherwise the patient will be deemed a non-responder.

The responders to the 9-HPT and/or JTT will be compared to the non-responders in relation to their changes in the DASH and AMSQ on treatment and off treatment at the baseline assessment. The change in the DASH and AMSQ in responders at Assessment 5 or 8 (week 10 or 20) will be compared to non-responders at that time-point.

Upper limb response will be examined at the end of treatment phase 1 and repeated at the end of the trial by comparing patients receiving active drug with those receiving placebo to assess any placebo effect and allow assessment of any residual beneficial effect on those who receive fampridine in treatment phase 1 and then switch to placebo in treatment phase 2. Response will again be considered as a 20% improvement in the 9HPT in the active treatment group compared with placebo and a 20% improvement from baseline in the time taken to complete all seven tasks in the JTT. See earlier comment

The responders to the T25FW will be compared to the non-responders in relation to their changes in the MSWS-12 on treatment and off treatment at the baseline assessment. The change in the MSWS-12 in responders at Assessment 5 or 8 (week 10 or 20) will be compared to non-responders at that time-point.

The patients’ scores on the MSIS-29 (physical) and SF-36 will be examined in relation to the objective changes (responder/non-responder) in the 9-HPT, JTT and the T25FW.

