13.2 DETERMINATION OF SAMPLE SIZE SUBJECTS

Given the previous reports, one would anticipate in this observational study that approximately 30+ % of patients would experience a significant (25%) improvement in indices of upper limb and walking mobility. Using a crossover design and treating the observations as paired within individuals, and allowing for loss to follow up during the trial, a sample size of 80 (40 in each arm) will be used.

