13.5 EFFICACY ANALYSIS

Primary efficacy endpoint:

An upper limb responder to fampridine will be defined as a patient with both of the two "on treatment" 9-HPT assessments (assessments 4 & 5 or 7 & 8) improving 20% from the average of the baseline assessments (1, 2 & 3).

Secondary efficacy endpoints:

- a) A secondary measure of upper limb responsiveness will be defined as a 20% improvement in from baseline in the average time taken to complete all seven tasks on the JTT “on treatment” (assessments 4 & 5 or 7 & 8) compared with baseline assessments (assessments 1,2 & 3).
- b) A mobility responder to dalfampridine will be defined as a patient with both of the two “on treatment” T25FW assessments (assessments 4 & 5 or 7 & 8) being better than the maximum of any of the four “off treatment” assessments (assessments 1, 2, 3, & 9). Otherwise the patient will be deemed a non-responder.
- c) The responders to the 9-HPT and/or JTT will be compared to the non-responders in relation to their changes in the DASH and AMSQ on treatment and off treatment at the baseline assessment. The change in the DASH and AMSQ in responders at Assessment 5 or 8 (week 10 or 20) will be compared to non-responders at that time-point.

Upper limb response will be examined at the end of treatment phase 1 and repeated at the end of the trial by comparing patients receiving active drug with those receiving placebo to assess any placebo effect and allow assessment of any residual beneficial effect on those who receive fampridine in treatment phase 1 and then switch to placebo in treatment phase 2. Response will again be considered as a 20% improvement in the 9HPT in the active treatment group compared with placebo and a 20% improvement from baseline in the time taken to complete all seven tasks in the JTT. See earlier comment

- d) The responders to the T25FW will be compared to the non-responders in relation to their changes in the MSWS-12 on treatment and off treatment at the baseline assessment. The change in the MSWS-12 in responders at Assessment 5 or 8 (week 10 or 20) will be compared to non-responders at that time-point.

The patients’ scores on the MSIS-29 (physical) and SF-36 will be examined in relation to the objective changes (responder/non-responder) in the 9-HPT, JTT and the T25FW.

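### No fampridine-versus-placebo test or estimate is attached to the primary 9-HPT responder endpoint; the general paired test has no period term, and the synopsis applies it to independent groups

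*Combined protocol and SAP*

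**What the plan says.** - **Objective (9.0):** to assess "PR-fampridine medication compared to placebo for upper limb function".
- **Primary endpoint (9.4, repeated in 10.3.2 and 13.5):** "The primary end point will be identifying an upper limb responder to fampridine". A patient responds if both 9-HPT tests in a treatment period meet the rule "improving 20% from the average of the baseline assessments (1, 2 & 3"). No test, effect measure or confidence interval stands beside it.
- **General method (13.1):** one sentence, in which outcome is assessed "using the Wilcoxon Signed Rank test to establish whether there is a difference between the paired 'on treatment' outcome measures for each individual". It names no outcome and does not say which two measurements form the pair.
- **Sample size (13.2):** reached by "treating the observations as paired within individuals" in a crossover.
- **Active versus placebo (9.4, 10.3.2, 13.5):** among the secondary endpoints, upper limb response is compared between patients on active drug and on placebo, at the end of phase 1 and again at the end of the trial. The 9-HPT rule there is a "20% improvement in the 9HPT in the active treatment group compared with placebo". No test is named.
- **Training (10.3):** the timed tests are repeated at the two baseline visits because training effects are expected.
- **Synopsis, statistical methods:** questionnaire changes in responders and non-responders are compared by the signed-rank test.

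**The concern.** A responder rule that looks only at change from baseline counts a patient who improved through practice or placebo response in the same way as one helped by the drug. It answers the stated objective only once placebo-period response is scored by the same rule and the two are compared. The plan does not say how that is done for the primary endpoint or which effect is reported.

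Section 13.1 may be meant to supply the comparison. But 9.4 uses the on-treatment label for the two visits within one period (4 & 5, or 7 & 8), so the pair can be read in two ways. On the natural reading, fampridine period against placebo period, the test ignores period. Both periods are scored against assessments 1–3, and by assessment 7 the patient has already taken the 9-HPT six times. Any practice gain therefore falls more on period 2.

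The synopsis raises a separate problem: responders and non-responders are different people, so a paired test cannot be applied to them.

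**Working it through.** **The plan's own figure.** The 80 patients in 13.2 cannot be reproduced, because power, placebo response rate, within-patient discordance and dropout rate are not given. The point does not depend on that figure.

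**What 13.1 amounts to on a yes/no outcome.** On 0/1 pairs the signed-rank test is McNemar's test without continuity correction. With 20 against 7 discordant pairs, z = (20 − 7)/√27 = 2.50, and both tests give p = 0.0124. So 13.1 could be applied to responder status, although the plan does not say that it is.

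**Effect of leaving period out.** Let τ be the treatment effect and π the period effect, both in SDs of the within-patient difference. The mean fampridine-minus-placebo difference is τ − π in sequence A (fampridine first) and τ + π in sequence B. With nA and nB completers:

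- Unadjusted mean = τ + π(nB − nA)/(nA + nB).
- Mean averaged over the two sequences = ½[(τ − π) + (τ + π)] = τ.
- With nA = nB the unadjusted estimate is unbiased, but π adds π² to the variance of the pooled differences. The SD rises from 1 to √1.25 = 1.12 at π = 0.5 and to √2 = 1.41 at π = 1.0. This makes the test conservative.
- At 40/35 and π = 0.5 the shift is 0.5 × (−5/75) = −0.033 SD. At 40/30 it is 0.5 × (−10/70) = −0.071 SD, so a true 0.35 is estimated as 0.28. At 30/40 it is estimated as 0.42.

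**Simulation for times** (normal differences, two-sided 5%). The unadjusted test is signed-rank. The adjusted test is rank-sum on period 1 minus period 2 differences between sequences. All effect sizes, period effects and completer numbers are assumptions.

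Type I error, unadjusted:

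| Completers A/B | π = 0.2 | π = 0.5 | π = 1.0 |
|---|---|---|---|
| 40/40 | 4.7% | 2.6% | 0.4% |
| 40/35 | 4.6% | 3.4% | 1.2% |
| 40/30 | 5.0% | 5.7% | 5.3% |
| 40/28 | 5.3% | 7.0% | 9.0% |
| 40/25 | 6.0% | 11.0% | 18.6% |

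At period effects of 0.5 and 1.0 SD the adjusted test stays at 4.6–5.6%.

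Power at τ = 0.35, unadjusted against adjusted:

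- 40/40: essentially equal at π = 0.2; 79% v 85% at 0.5; about 55% v 85% at 1.0.
- 40/35: about 67% v 83% at 0.5.

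**Simulation for responders** (assumed 15% on placebo, 30% on fampridine; logit model with patient SD 1.5), McNemar against Prescott at 40/40:

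- practice gain of 5 points: 78.3% v 77.4%
- practice gain of 10 points: 79.1% v 79.4%
- practice gain of 20 points: 76% v 80%

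The 30% in 13.2 refers to a 25% improvement in upper limb and walking indices, so it is not an input for this 20% endpoint.

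**How likely are unequal sequences?** With the same random dropout of 15–25% in both sequences, a gap of 5 or more has probability 16–24%, and a gap of 10 or more 0.3–1.4%. Dropout that depends only on the product does not separate the sequences, because every patient is due both products. With 15% lost on fampridine and 5% on placebo, expected completion is 0.85 × 0.95 = 80.75% in A and in B, and a gap of 10 or more has a chance of about 0.7%.

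**The case against.** The plan is not silent on placebo. Sections 9.4, 10.3.2 and 13.5 do compare upper limb response on active drug with that on placebo, which implies that placebo-phase response is looked at. The phase 1 part of that comparison is between groups within one period, so neither period nor carry-over can disturb it. A reader might infer that the trial has no active-versus-placebo comparison of upper limb function; the documents do not support that. What stands is that this comparison is secondary, uses another response rule, and has no test or estimate.

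Sections 13.1 and 13.2 together point to a paired drug–placebo test, so part of the remedy is clarification. That is accepted.

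The repeated baseline tests in 10.3 can also be read as mitigation: training is meant to be used up before randomisation, and nothing shows that large gains persist between weeks 6–10 and 16–20. This is fair, and it is why the 0.2 SD row belongs in the table. But the plan does not show that the run-in is enough.

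A reader might further infer that withdrawals under 10.5, with the complete-case analysis in 13.9, inflate type I error. The documents do not support this either. Product-dependent withdrawal leaves the sequences balanced in expectation; 10.5 asks patients who discontinue to stay in follow-up; and 13.3 calls the primary analysis intention to treat, which itself needs reconciling with 13.9.

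Finally, the Prescott and rank-sum tests are one valid choice among several. The need is for some named, period-adjusted method.

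**Conclusion.** The point holds in this form. The primary endpoint has no fampridine-versus-placebo test or estimate attached; the general test neither defines its pair nor adjusts for period; and the synopsis test is wrong as written for two independent groups. The synopsis error touches only the secondary questionnaire analyses (MSWS-12, MSIS-29, DASH, AMSQ).

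The expected harm from omitting period is lost power, not false positives. With equal completers and an assumed 0.35 SD effect the loss runs from essentially nothing at a 0.2 SD period effect, through 6 points at 0.5 SD, to about 30 points at 1.0 SD. An ordinary chance imbalance of 40/35 at 0.5 SD widens it to about 16 points and shifts the estimate by 0.033 SD. Type I error clearly above 5% needs both a large period effect and a completer gap of about 12 or more, and nothing in the documents makes that likely. This should be fixed before unblinding. It does not make the design invalid.

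**What to change.** 1. **Section 13.5.** Score the 20% rule for every patient in both periods (assessments 4 & 5 and 7 & 8, each against the mean of assessments 1–3). Compare fampridine-period with placebo-period response within patients, adjusted for period, for example by the Prescott test. Report the difference in responder proportions averaged over sequences A and B with a 95% CI, where SE = ½√(sA²/nA + sB²/nB); simulated coverage was about 94–95%. Keep the phase-by-phase comparison as supportive, and reconcile its response rule with the primary one.
2. **Section 13.1.** Define the pair as fampridine period versus placebo period. For times, compare period 1 minus period 2 differences between sequences by the Wilcoxon rank-sum test. State that the analysis assumes no carry-over, since 9.4 itself anticipates a "residual beneficial effect on those who receive fampridine in treatment phase 1".
3. **Synopsis.** Replace signed-rank with rank-sum for responders versus non-responders.

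**Cost.** Wording only; no new data, visits or patients. If there is no period effect, adjustment loses about 0–4 power points (responders, 15% v 30%: 74.5% to 73.1% at 40/40 and 65.4% to 61.5% at 25/40; times: 0 points at 40/40 and 3 at 40/25). The adjustment does not remove carry-over. An assumed 0.2 SD residual effect in sequence A lowers the averaged estimate by half of it, from 0.35 to 0.25 SD, and power from 85% to 57%.
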